## 2.7.5 Other safety data

## 2.7.6 Ocular evaluations

The number of patients with available assessment for each type of ocular evaluation and eye side will be provided for Safety Set 4 if not otherwise stated. The frequency and percentage of subjects with completed ocular assessments will be presented by eye side, evaluation type, timepoint, and treatment arm. Additionally, a summary for the number of ocular examinations performed at each time point will be presented by treatment arm. Overall interpretation for ocular will be listed.

As color fundus photography and Lens opacification grading (LOCSIII) was only implemented with protocol amendment 6 and never reported so far, these analyses will also be provided for Safety set 1 to 3. A separate listing for subjects with available images of color fundus photography and LOCSIII will be provided.

### 2.7.6.1 Visual acuity

Visual acuity will be measured using the Snellen visual acuity. This is determined by establishing the smallest optotypes that can be identified correctly by the patient at a given observation distance. Snellen visual acuity can be reported as a Snellen fraction (m/M) in which the numerator (m) indicates the test distance and the denominator (M) indicates the distance at which the gap of the equivalent Landolt ring subtends 1 minute of arc. The following formula for conversion from Snellen acuity results to the logMAR score (Holladay 1997) will be applied and the LogMAR score will be calculated for each timepoint:

$$\text{logMAR score} = -\log_{10}(m/M).$$

The logMAR scores will be categorized as follows: < 0.1,  $\geq 0.1$  to < 0.2,  $\geq 0.2$  to < 0.3,  $\geq 0.3$  to < 0.6,  $\geq 0.6$ . The following shift tables will be generated using the above categories by treatment group:

- Comparing baseline and *increases* from baseline in logMAR score category at each visit by eye side (right & left)
- Comparing baseline and *decreases* from baseline in logMAR score category at each visit by eye side (right & left)

Change from baseline (logMAR) = Post Baseline Value (logMAR) – Baseline Value (logMAR)

In case both values are negative, the absolute values of Post baseline & Baseline records will be used for the calculation.

The number and percentage of subjects with the following change from baseline for logMAR categories (< 0.1,  $\geq 0.1$  to < 0.2,  $\geq 0.2$  to < 0.3,  $\geq 0.3$  to < 0.6,  $\geq 0.6$ ) will be summarized by treatment arm:

- the best change (decrease) in logMAR score category from baseline by eye side (right, left, best)
- the worst change (increase) in logMAR score category from baseline by eye side (right, left, worst)

The changes from baseline at each visit will be calculated for assessments done in the same correction method as at baseline.

The shift tables and summaries will be produced for the Safety set 4.

A listing with the Snellen fraction, logMAR score abnormalities and change from baseline categories will be provided for all subjects.

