### Visual acuity

Visual acuity will be measured using the Snellen visual acuity. This is determined by establishing the smallest optotypes that can be identified correctly by the patient at a given observation distance. Snellen visual acuity can be reported as a Snellen fraction (m/M) in which the numerator (m) indicates the test distance and the denominator (M) indicates the distance at which the gap of the equivalent Landolt ring subtends 1 minute of arc. For each timepoint, the LogMAR score will be calculated as  $-\log(m/M)$ .

Descriptive statistics of the LogMAR scores at baseline, at each post-baseline visit and changes from baseline at each post-baseline visit will be presented, for each eye by treatment group provided that for a given patient, the assessment was done in the same condition (with/without correction) as done at baseline.

The LogMAR value will be compared at baseline and worst post-baseline based on the identifying clinically meaningful deterioration in LogMAR of  $\leq 0$ ,  $> 0$  to  $< 0.1$ ,  $0.1$  to  $< 0.2$ ,  $0.2$  to  $< 0.3$  and  $\geq 0.3$ , for each eye side by treatment group.

Number and percentage of patients with clinically relevant LogMAR change from baseline more or equal than 0.2 and more or equal than 0.3 will be summarized by treatment arm. For patients with such values, a listing will also be provided.

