#### **Visual acuity**

Visual acuity will be measured using the Snellen visual acuity. This is determined by establishing the smallest optotypes that can be identified correctly by the patient at a given observation distance. Snellen visual acuity can be reported as a Snellen fraction (m/M) in which the numerator (m) indicates the test distance and the denominator (M) indicates the distance at which the gap of the equivalent Landolt ring subtends 1 minute of arc. The following formula for conversion from Snellen acuity results to the logMAR score (Holladay 1997) will be applied and the LogMAR score will be calculated for each timepoint.

$$\text{logMAR score} = -\log_{10}(m/M).$$

LogMAR scores will be categorized as follows: <0.1, ≥0.1 to <0.2, ≥0.2 to <0.3, ≥0.3 to <0.6, ≥0.6. Shift tables using these categories to compare baseline to increases and decreases from baseline of logMAR score will be presented at each visit, for each eye side by treatment group in the core phase. Number and percentage of patients with worst change from baseline for each logMAR category will be summarized by treatment arm. Changes from baseline at each visit will be calculated for assessments done in the same condition (with/without correction) as at baseline. The shift tables and summaries will be repeated for the safety set 4.

A listing with the Snellen fraction and logMAR score will be provided for all patients with a flag for patients who have 0.2 or more increase in the post-baseline logMAR score.

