### **2.7.7 Growth and Development**

**Growth velocity** will be listed at EOT-extension visit and summarized using descriptive statistics by sex and age group during the entire granule period for the Safety Set 4. Listing will be produced for the entire granule period on the Safety Set 4.

The growth velocity in height which evaluates the rate of growth per year will be calculated on the difference with the previous measure of height (in cm) and the time period (in days) as:

$$\text{Growth velocity (cm / year)} = \frac{(height V_x - height V_{x-1}) * F}{date V_x - date V_{x-1}}$$

(with  $V_x$  = actual visit ;  $V_{x-1}$  = previous visit ;  $F = 365.25$ ).

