### 2.7.7.1 SDS method

**Growth data** collected during the study (both core and extension phases) for safety set 4 subjects will also be summarized descriptively at each relevant time point. These data consist of BMI, height, height velocity, weight and weight velocity.

The baseline for this analysis will be the core phase baseline for both DT crossover and granule patients.

Height and BMI will be summarized at 6 months intervals, using the standard deviation scores (SDS, also called z-score), velocity and velocity SDS. The relevant height and weight values for each 6-month period are defined using time windows, as defined in [Section 5.3.3](#). The z-scores will allow identification of potential outliers.

The formula used to calculate the SDS and height and weight velocities are provided in [Section 5.6](#).

Note that BMI SDS are reported instead of weight SDS as no reference data for weight are provided by the WHO for age beyond 10.

Height/BMI SDS and height/weight velocity SDS will be summarized using descriptive statistics (mean, standard deviation, range) for each time window (at Baseline and thereafter allowing informal comparison of growth data), as well as by presenting number of patients with SDS values lower/higher than 5th/95th percentiles respectively. Box plots will also be plotted for each time window. In addition, a shift table to compare baseline SDS to the worst on-treatment SDS will be produced for height and BMI SDS. All height/BMI SDS, velocity and velocity SDS data will be listed, and values of SDS and velocity SDS outside of the central 95% of population values will be flagged as either High (SDS > 1.645) or Low (SDS < -1.645).

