## 5.6 Growth data

SDS will be calculated using the current formulae provided by the WHO as follows:

1. Calculate  $z_{\text{ind}} = \frac{\left(\frac{x}{m}\right)^L - 1}{s}$
2. If  $|z_{\text{ind}}| \leq 3$ ,  $SDS = z_{\text{ind}}$   
If  $z_{\text{ind}} > 3$ ,  $SDS = 3 + (X - SD3pos) / SD23pos$   
If  $z_{\text{ind}} < -3$ ,  $SDS = -3 + (X - SD3neg) / SD23neg$

where:

- $X$  is height in centimeters or BMI in kilograms/ $\text{m}^2$ ,
- $L, M$  and  $S$  are height or BMI-, sex- and age-specific reference values from the WHO Growth Charts.

- SD3pos is the cutoff 3SD calculated by the LMS method:  
$$SD3_{pos} = M * (1 + LS*3)^{1/L}$$
- SD3neg is the cutoff -3SD calculated by the LMS method:  
$$SD3_{neg} = M * (1 + LS*(-3))^{1/L}$$
- SD23pos if the difference between the cutoffs 3SD and 2SD:  
$$SD23_{pos} = M * (1 + LS*3)^{1/L} - M * (1 + LS*2)^{1/L}$$
- SD23neg if the difference between the cutoffs -2SD and -3SD:  
$$SD23_{neg} = M * (1 + LS*(-2))^{1/L} - M * (1 + LS*(-3))^{1/L}$$

Height-for-age and BMI-for-age L, M and S reference values for males and females are available under <http://www.who.int/childgrowth/standards/en/> (for patients aged between 0 to 5 years old) and <http://www.who.int/growthref/en/> (for patients aged between 5 to 19 years old). These correspond to the latest available international references available at this time and described in the 2007 Bulletin of the World Health Organization ([Mercedes de Onis et al 2007](#)). The age category immediately above the patient's exact age should be used. SDS is actually a Z score that measures the distance from the population mean in units of standard deviations. That is, SDS  $\leq -1.645$  refers to values in the lowest 5%. (The usual percentile more commonly used in the clinical practice can be derived from the z-score by a normal distribution).

Note that BMI is reported instead of weight as no reference data are provided by the WHO for age beyond 10.

Height velocity is defined as follows:

Height velocity (cm/6-months) = (height in time window  $k$  – height in time window  $k-1$ )  $\div$  ([assessment date in time window  $k$  – assessment date in time window  $k-1$ ]  $\times$  [365.25/2]),

and similarly for weight velocity.

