Velocity SDS is calculated as (velocity – mean) / SD, where mean and SD are obtained as the height-, weight-, sex- and age-specific values ([Baumgartner et al 1986](#)), where the age category immediately above the patient's exact age (at the assessment date in time window  $k$ ) should be used. Velocity SDS will only be calculated for time window  $k$  if data also exists for time window  $k-1$ , since calculating across multiple units of 6 months requires more than one reference value to be taken into account.

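### The final SAP's visual acuity rule reverses the sign of change when both logMAR values are negative, and the 6-month growth velocity formula as printed does not give its stated unit

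*SAP*

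**What the plan says.** **Visual acuity (final CSR SAP, 2.7.6.1).** logMAR is −log10(m/M), so acuity better than 20/20 gives a negative score and a lower score is better. Change is post-baseline minus baseline. Summaries include "the worst change (increase) in logMAR score category from baseline by eye side (right, left, worst") and the matching best change, which is a decrease. There are also shift tables for increases and for decreases. One exception follows the change formula: "In case both values are negative, the absolute values of Post baseline & Baseline records will be used for the calculation".

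The two other SAPs have no such exception. The primary analysis SAP (2.9.2, Visual acuity) counts patients with "clinically relevant LogMAR change from baseline more or equal than 0.2 and more or equal than 0.3". The End of Core Phase SAP (2.9.6, Visual acuity) plans a listing with "a flag for patients who have 0.2 or more increase in the post-baseline logMAR score".

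**Growth velocity (final CSR SAP, 5.6 and 2.7.7).** Section 5.6 begins "Height velocity (cm/6-months) = (height in time window". As printed, it divides the height difference by the product of the date difference and 365.25/2, and weight velocity is to follow the same form. Section 2.7.7 has an annual measure that "evaluates the rate of growth per year will be calculated on the difference with the previous measure of height"; there 365.25 multiplies the height difference. The 6-month velocity feeds a standardised score: "Velocity SDS is calculated as (velocity – mean) / SD".

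**Flagging (final CSR SAP, 2.7.7.1).** Values "outside of the central 95% of population values will be flagged as either High (SDS > 1.645") or, symmetrically, Low below −1.645.

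**The concern.** Ordinary subtraction already handles negative scores, so the exception is not needed. Taking absolute values first turns the scale round: among negative scores the better eye has the larger absolute value. An eye that loses acuity but stays better than 20/20 is counted as improved, and an eye that gains is counted as worse.

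These tables are part of the ocular safety evaluation, which Protocol Amendment 6 was mainly written to support after a Health Authority request. The End of Core Phase SAP planned the same kind of shift tables and summaries for Safety Set 4 without the exception. The same eye at the same visit could therefore appear as a worsening in one report and an improvement in the next.

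The velocity formula raises a different risk. If programmed literally, every velocity is close to zero and the velocity SDS is about −mean/SD for every child.

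**Working it through.** **1. Sign of the acuity change**

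Inputs: the logMAR definition, the change formula and the exception, all from final SAP 2.7.6.1. The Snellen fractions are illustrative.

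For post P < 0 and baseline B < 0, |P| = −P and |B| = −B. So |P| − |B| = −P + B = −(P − B). The size of the change is kept and its direction is reversed.

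Scores from −log10(m/M): 20/10 = −0.3010; 20/12.5 = −0.2041; 20/16 = −0.0969; 20/20 = 0; 20/25 = +0.0969.

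| Baseline to post | Post − baseline | SAP as written | Effect |
|---|---|---|---|
| 20/10 to 20/16 | +0.2041 | −0.2041 | loss shown as gain |
| 20/12.5 to 20/16 | +0.1072 | −0.1072 | loss shown as gain |
| 20/16 to 20/12.5 | −0.1072 | +0.1072 | gain shown as loss |
| 20/16 to 20/10 | −0.2041 | +0.2041 | false worsening in the ≥0.2 to <0.3 category |
| 20/16 to 20/16 | 0 | 0 | unaffected |
| 20/10 to 20/20 | +0.3010 | +0.3010 | exception not triggered |
| 20/16 to 20/25 | +0.1938 | +0.1938 | exception not triggered |

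The first and sixth rows show a discontinuity. From 20/10, the smaller loss is tabulated as an improvement and the larger loss as a worsening.

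Reach: a hidden loss of at least 0.1 needs a baseline below −0.1, that is, better than 20/(20 × 10^−0.1) = 20/15.9. A hidden loss of at least 0.2 needs a baseline better than 20/(20 × 10^−0.2) = 20/12.6. In both cases the post-baseline value must still be better than 20/20.

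**2. Six-month velocity**

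Inputs: the formulas in final SAP 5.6 and 2.7.7, an illustrative gain of 3 cm, and 168 days between assessments (the spacing of the growth windows in Table 5-5, for example days 85–252 and 253–420).

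- Annual formula (2.7.7): 3 × 365.25 / 168 = 6.522 cm/year. Half of this is 3.261 cm per 6 months.
- Section 5.6 as printed: 3 / (168 × 182.625) = 0.0000978, in cm/day² rather than cm per 6 months.
- Section 5.6 with the factor as a multiplier: 3 × 182.625 / 168 = 3.261 cm per 6 months, which agrees with the annual formula.
- Ratio of the last two: 182.625² = 33,352.

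**3. Flagging limits**

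Φ(−1.645) = 0.050, so 2 × 0.050 = 0.100 lies outside ±1.645 and the interval is the central 90%. The same paragraph of 2.7.7.1 counts values beyond the 5th and 95th percentiles, and 5.6 describes −1.645 as marking the lowest 5%. The cut-off is therefore the intended one and only the percentage is wrong.

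**The case against.** The algebra cannot be disputed; the arguments on the other side concern reach and weight.

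- **Shift tables.** Every negative score lies in the lowest category, <0.1. If the shift tables compare score categories, an eye negative at both visits shows no shift and the exception does nothing there. The wording leaves some room for this. However, the change formula stands directly beneath the shift-table bullets, and the End of Core Phase SAP describes its tables as increases and decreases in the score. The best and worst change summaries are the clearer target in any case.
- **Narrow reach.** The effect depends on chart lines that the documents do not give. If the only lines better than 20/20 were 20/15 and 20/10 (an assumption), the largest reversal would be between −0.125 and −0.301, or 0.176. With 6/5 and 6/4 (also an assumption) it would be 0.097, inside the <0.1 category. A fall to 20/20 or worse at any visit is tabulated correctly at that visit. The 0.2 threshold comes from the two other SAPs; the final SAP uses it only as a category boundary. All of this stands and limits the size, not the error.
- **Other safeguards.** Snellen fractions are listed, and ocular findings that qualify as adverse events are recorded as such (Protocol 7.2.4.5). That is true, but the listing also carries the derived change categories, and the summary tables remain wrong.
- **Velocity.** The intended unit is printed beside the formula, other notation in 5.6 is irregular, programming specifications sit in a separate document, and near-zero velocities would be noticed at once. This is fair: it may be a typing or extraction slip, and it calls for a check of the source and programs.
- **Percentage wording.** This is editorial and adds no weight.

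**Conclusion.** The acuity rule is wrong as written. It reverses the direction of every non-zero change in eyes better than 20/20 at both visits and leaves all other eyes alone. With chart lines such as 20/16 and 20/10, the reversal reaches 0.204 in either direction, enough to create a false worsening of 0.2 or more or to hide a real one. The share of eyes affected cannot be derived from the documents.

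The velocity formula as printed contradicts both its own unit and the placement of the time factor in 2.7.7. Whether any output is wrong depends on how it was programmed. If it was programmed literally, the number of children flagged Low depends on reference means and SDs that the documents do not give.

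All affected outputs are descriptive safety summaries in the final CSR. In the final SAP the acuity tables are for Safety Set 4 only, and the co-primary endpoints are not touched. The point should be fixed, but it does not threaten the trial's main conclusions.

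**What to change.** - **2.7.6.1:** delete the absolute-value sentence and use post-baseline minus baseline whatever the signs.
- **5.6:** write velocity = (height in window k − height in window k−1) × (365.25/2) / (date in window k − date in window k−1), and the same for weight.
- **2.7.7.1:** replace 95% with 90% and keep ±1.645.
- Check the programming specification and the programs against all three. If acuity tables have already been produced under the exception, rerun them.

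The cost is one deleted sentence, one formula, one number and a program check. No new data are needed.

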## Amendment 6 (24-Jun-2021)

### Amendment rationale

As of 24-Jun-2021, 67 patients are ongoing in the extension phase of the study. All patients had completed the Core phase of the study by 18-Dec-2018. The primary analysis for this study was completed on 07-Dec-2018 (data cut-off date 31-May-2018).

The main purpose of this amendment is to introduce the requirement for central collection and assessment of photographs from ocular examinations (lens photographs and wide angle fundus photographs) collected during the study by a Novartis designated imaging Contract Research Organization (CRO). This change is in response to a Health Authority request to submit CALYPSO ophthalmic data (for up to 2 years of follow up) to support the ocular safety evaluation of deferasirox.

Clarification was also added to state that for patients who need correction, the best corrected visual acuity should be tested when performing the distance visual acuity test and that the corrected visual acuity should be documented in the source records.

In addition, mitigation procedures have been implemented throughout the protocol to ensure participant safety and trial integrity during a Public Health emergency, as declared by Local or Regional authorities i.e. pandemic, epidemic or natural disaster.

Finally, assessment of the study Risk/Benefit in light of the ongoing coronavirus disease 2019 (COVID-19) pandemic at the time of this protocol amendment concluded that there are no additional risks related to COVID-19 for this study. Patient with cytopenias are more susceptible to infections in general, compared to patients without cytopenias. There have been postmarketing reports of cytopenias in patients treated with deferasirox and patients with cytopenias may be at higher risk of COVID-19 with a poorer prognosis. The periodic monitoring of blood counts and interruption of study treatment in patients who develop unexplained cytopenia, as defined in the protocol, are expected to mitigate this risk.

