#### **7.2.4.5 Ocular Examination and Central Imaging Assessment**

Patients will undergo ophthalmologic examinations during the core phase at Visit 1, 11, 777 (EOT Core) and at unscheduled visits (if needed). During the optional extension phase, assessments will be done annually as per Exjade prescribing information and at EOT of Extension phase.

The ophthalmologic examination includes the following assessments:

- Distance visual acuity test: in patients who don't need correction with glasses or contact lenses, visual acuity test may be performed without correction. In patients who need correction (either wears prescription glasses/contact lenses or uncorrected visual acuity is not within normal limits), best corrected visual acuity should be tested. Information about visual acuity without correction, best corrected visual acuity and prescription/correction must be documented in the source records.
- Applanation tonometry
- Slit Lamp exam and lens photography
- Fundus exam and wide angle fundus photography of the retina and optic nerve

Interpretation of the ocular examinations must be made by a qualified physician and documented on the CRF page.

Information about the results of the ocular examinations, including the lens photographs and the wide angle fundus photographs of the retina and optic nerve, must be present in the source documentation at study site. Significant findings of the ocular examinations that meet the definition of an AE must be recorded in the adverse event summary page of the case report form.

All screening and on-study wide angle fundus photographs and lens photographs, including photography acquired prior to the release of Protocol Amendment 6, must be sent to an imaging Contract Research Organization (CRO) designated by Novartis for central assessment.

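### The same-method rule for visual acuity change can lose a child's change value because acuity worsened, unless the uncorrected value is also in the database

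*SAP*

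**What the plan says.** Final SAP 2.7.6.1 plans, on Safety Set 4, by-visit shift tables of logMAR increases and decreases, and tables of best and worst change from baseline by eye. It then sets a matching condition: "The changes from baseline at each visit will be calculated for assessments done in the same correction method as at baseline". The End of Core Phase SAP (2.9.6, Visual acuity) has the same condition, limiting change to "assessments done in the same condition (with/without correction) as at baseline". The final SAP gives no rule for a patient whose method changes after baseline and no count of such patients.

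Protocol 7.2.4.5 decides which method is used. For a patient who needs no glasses or lenses, the "visual acuity test may be performed without correction". A patient counts as needing correction if glasses or lenses are worn, or if "uncorrected visual acuity is not within normal limits), best corrected visual acuity should be tested". The next sentence bears directly on this point: "Information about visual acuity without correction, best corrected visual acuity and prescription/correction must be documented in the source records".

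The Amendment 6 rationale presents the best-corrected wording as a clarification, dated 24-Jun-2021, when "67 patients are ongoing in the extension phase of the study".

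Final SAP 2.1.1 takes the number of patients in the arm as the percentage denominator. Final SAP 5.3.4 uses all on-treatment values for the worst post-baseline assessment.

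**The concern.** For a child tested uncorrected at baseline, the event that switches the method is uncorrected acuity leaving the normal range. The SAP's condition for computing a change then fails for the new method. Whether a change value exists can therefore depend on the outcome that it is meant to measure.

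Amendment 6 answers a health authority request for ophthalmic data on deferasirox, and protocol Table 6-2 notes reports of lens opacities with the drug. The acuity change tables are the planned summary of visual function. If worsened children lose their change value but stay in the denominator, those tables understate deterioration and show no sign that anything is missing.

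**Working it through.** The plan states no figure on this point, so there is none to reproduce. The check sets the two rules side by side and then applies the SAP's formula to assumed values.

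**1. Who can be affected**

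| Child | Method at baseline → later | Same-method change |
|---|---|---|
| Corrected at baseline | corrected → corrected | computed |
| Uncorrected, stays within normal limits | uncorrected → uncorrected | computed, including any worsening within those limits |
| Uncorrected, later abnormal, both values in database | uncorrected → both | computable from the uncorrected value |
| Uncorrected, later abnormal, only best-corrected value in database | uncorrected → best-corrected | none from that visit on |

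Only the last row is lost. Which of the last two rows applies depends on whether the uncorrected value required in source records also reaches the database. Protocol Table 7-2 marks the ocular examination as database data, but no document says that both acuity values are entered.

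**2. One child (assumed acuities)**

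Formula from final SAP 2.7.6.1: logMAR = −log10(m/M).

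- Baseline, uncorrected 20/20: −log10(1) = 0.00.
- Later, uncorrected 20/50: −log10(0.4) = 0.398.
- Later, best-corrected 20/20: 0.00; or best-corrected 20/32: −log10(0.625) = 0.204.

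If the uncorrected value is captured, the change is 0.398 − 0.00 = +0.398, in the ≥0.3 to <0.6 category. If only the best-corrected value is captured, no change is computed. Dropping the matching rule is not a remedy: the cross-method change would be 0.00 or +0.204, which hides or shrinks the loss.

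**3. Effect on a reported share (illustration)**

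Take N = 67 as one group, with w children truly worsened and a fraction s of them without a same-method value at the visit. Both w and s are assumptions.

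- Arm denominator: w(1 − s)/N.
- Evaluable denominator: w(1 − s)/(N − ws).
- Example with w = 7, s = 0.5: 3.5/67 = 5.2%; 3.5/63.5 = 5.5%.

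| w (true share) | s = 0.25 | s = 0.5 | s = 0.75 | s = 1 |
|---|---|---|---|---|
| 3 (4.5%) | 3.4% / 3.4% | 2.2% / 2.3% | 1.1% / 1.2% | 0% / 0% |
| 7 (10.4%) | 7.8% / 8.0% | 5.2% / 5.5% | 2.6% / 2.8% | 0% / 0% |
| 13 (19.4%) | 14.6% / 15.3% | 9.7% / 10.7% | 4.9% / 5.7% | 0% / 0% |

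Cells show arm / evaluable denominator; at s = 0 both equal the true share. On the arm denominator, reported/true = 1 − s for any N. This matters because Safety Set 4 is everyone who ever received granules, not just these 67. The evaluable denominator recovers little, because the children removed are the worsened ones. It has to be shown with the count of missing pairs.

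**4. Worst-change table**

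Matched visits before a switch still count. By the protocol's trigger, uncorrected acuity was within normal limits at those visits. A switched child may therefore appear with a small worst change rather than as missing, and an evaluable denominator would not reveal this.

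**The case against.** A reader might infer that children whose sight worsens simply disappear from the change tables. The documents do not support that.

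- The uncorrected value must be documented in source, and finding it abnormal means that it was measured. The SAP condition can be read as selecting the matching assessment where two exist. This stands: if both values are in the database, nothing is lost.
- Children corrected at baseline, worsening within normal limits and all matched visits before a switch are unaffected. This stands.
- Affected children remain visible: "A listing with the Snellen fraction, logMAR score abnormalities and change from baseline categories will be provided for all subjects". Final SAP 2.7.6 also counts completed assessments by eye, type, timepoint and arm. Slit lamp, lens photography and fundus analyses do not use the matching rule. This stands in part. A mismatched visit has no change category to list, completed assessments are not the same as pairs evaluable for change, and structural findings do not measure acuity. The End of Core Phase listing flagged logMAR increases of 0.2 or more; the final SAP names no such flag.
- The wording that "the best corrected visual acuity should be tested when performing the distance visual acuity test" dates from June 2021. The authority asked for up to 2 years of follow-up. The core phase was complete by 18-Dec-2018, so two years from extension entry end by about December 2020. This limits the bearing on that request, but the final tables cover the entire granule period.

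Two further inferences also go too far. One is that glasses wearers with an uncorrected baseline form a second lost group. The baselines of the 67 do predate the clarification, but earlier testing practice is not stated. The other is that best-corrected acuity should become the main scale. A normal uncorrected baseline is not necessarily best-corrected, and the example in the working shows a refractive loss of 0.398 reduced to 0.00.

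**Conclusion.** The point holds conditionally. The two rules together allow a change value to be missing because acuity worsened, and the final SAP neither prevents nor reports this. It applies to children tested uncorrected at baseline whose uncorrected acuity later becomes abnormal, from that visit onward, and only if the uncorrected value is not in the database.

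The bias is toward no deterioration. Its size runs from zero (both values captured) to complete loss of the worsened group (every worsened child switched, only best-corrected acuity captured, no earlier matched visit showing worsening). The documents give no switching rate, so no patient number can be put on it.

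These are descriptive safety tables with no test or decision rule attached. Matching on method is itself sound; what is missing is a rule for the switch.

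**What to change.** In final SAP 2.7.6.1:

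1. Keep same-method change as the main analysis and compute it within each method. At a switch visit, use the uncorrected value against an uncorrected baseline wherever it is available. Confirm whether both values are in the database.
2. Report by arm, eye and visit the number of patients with acuity assessed but no same-method pair, and use patients evaluable for change as the denominator.
3. Add a row by arm for new need for correction since baseline. This also catches switched children whose worst change comes only from earlier visits.
4. As a supplementary table, show the best-corrected acuity of switched children, with change against a baseline taken uncorrected because no correction was needed. Note that this comparison can hide a refractive loss.

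The cost is slightly more derivation work. If the uncorrected values were left in source records, some will have to be retrieved.
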